Cancer is a major public health problem worldwide. Cancer patients are often treated multiple times with chemotherapy, radiation, and/or biological therapy, interspersed with active surveillance. As a result, cancer patients and survivors carry physiological and psychological side effects, including muscle atrophy, weight changes, reduced aerobic capacity, decreased strength and flexibility, depression, fatigue, nausea, and an overall decrease in quality of life (Courneya et al., 2009; Siegel et al., 2023; Sung et al., 2021). Of all the side effects, cancer-related fatigue is the most common. It differs from normal fatigue in daily activities and affects up to 70% of cancer patients during chemotherapy and radiation therapy. In addition, sedentary habits lead to the development of a self-perpetuating cycle of fatigue, which results in increasing levels of catabolic processes at all levels (physical, emotional, social). Exercise interrupts this downward cycle and decreases cancer-related fatigue (Lucía et al., 2003). Exercise is recognized as one of the most effective nonpharmacological interventions to improve the quality of life of cancer survivors. (Meneses-Echavez et al., 2019; Mishra, 2014; Young-McCaughan & Arzola, 2007). Exercise, both during and after treatment, is an effective tool for improving functional capacity, muscle strength, functional mobility (i.e., improving balance will reduce the risk of falls and fractures), fatigue, psychological well-being (reducing the risk of anxiety and depression), and health-related quality of life in cancer patients and survivors (Dash et al., 2016). Evidence-based studies recommend resistance training and combined aerobic-resistance training interventions (Ficarra et al., 2022; Wang et al., 2023). The multicomponent training program has reported benefits in body composition and functional efficiency in cancer survivors (Bartolomeu et al., 2016).

PURPOSE AND HYPOTHESIS OF THE PROJECT

Primary outcome:

The purpose of this study is to evaluate the effectiveness of a multicomponent training protocol (MCT) on the following parameters: psychological, physical fitness, mental well-being, and quality of life, in cancer survivors currently in a stabilized condition, compared to an aerobic training protocol (AT) and a waiting control group (WLCG). In addition, the aim is to evaluate the impact of training in participants' coping strategies, i.e., the ways in which they manage stress, emotional difficulties and daily challenges, in order to foster better psychological adaptation and greater autonomy.

Secondary outcome:

To assess adherence to protocols through analysis of dropout rates and number of sessions completed.

Hypothesis

We hypothesize that both groups will demonstrate improvements in physiological parameters, physical fitness, mental well-being, and overall quality of life compared to the WLCG. Furthermore, the MCT group is expected to achieve greater enhancements in physiological parameters than the AT group. Additionally, the MCT group is anticipated to have a more significant impact on strengthening coping strategies, promoting better stress management, and fostering more effective psychological adaptation.

PARTICIPANTS

The study aims to recruit at least 60 cancer survivors currently in physiological or chronic-stabilized condition between 18-80 years of age.

Inclusion criteria.

- Women/Men;
- Age between 18 and 80 years at the time of initial treatment;
- Subjects in remission for at least 3 months;
- No diagnosis of secondary cancer at baseline;
- No physical impediment to physical activity (Eastern Cooperative Oncology Groups (ECOG) performance status 0-1);
- Signature of a written informed consent form (or their legally recognized representatives must sign) indicating that the patient understood the purpose and procedures required for the study and is willing to participate in the study;
- Sedentary lifestyle (subjects who have not followed WHO guidelines for aerobic and resistance exercise in the past 3 months).
- Currently in treatment, as long as not hospitalized, in stabilized chronic condition,
- Positive medical specialist assessment of noncompetitive physical activity practice.

Exclusion criteria.

- Metastasis;
- Uncontrolled hypertension or untreated heart disease;

- Severe musculoskeletal or joint disorders with severe mobility limitations;
- Psychiatric disorders;
- Taking psychotropic drugs;
- Inability to engage in physical activity;
- Lack of fitness to practice sports.
- Expected absence of more than two weeks during the intervention period.

SAMPLE NUMEROSITY

G*Power software (version 3.1) was used to determine the sample size needed to ensure adequate statistical power.

The calculation was performed assuming a mean effect (with a value of 0.25 for effect size f), which is a value commonly used in studies of similar size. A significance level of 0.05 was set and a statistical power of 85% (0.85) was adopted, which is generally considered an adequate value to minimize the risk of type II errors.

For the calculation, two groups (multicomponent training and aerobic training) and two measurement times (before and after the intervention) were considered. An average correlation (0.5) was estimated between the repeated measurements on participants, as it is expected that the collected data are fairly correlated between the different surveys. Finally, it was assumed that there were no violations of sphericity by setting a correction for nonsphericity equal to 1.

Based on these parameters, the calculation indicated the need for a sample size of 32-40 total participants, with 16-20 participants per group, to ensure sufficient statistical power to detect any significant effects.

PROCEDURES

Participants will be recruited through days dedicated to raising awareness and promoting the project, also organized in the area in collaboration with relevant bodies, associations and health facilities. During these events, detailed information will be provided on the objective of the study, potential benefits, and how to participate. Informational materials, such as brochures and posters, will also be used and distributed at major gathering places. Then participants will be randomly assigned to one of three groups:

- MCT
- AT

- WLCG

Data collection

Prior to the intervention, all subjects will sign an informed consent upon authorization from their attending physician. All subjects will participate in physiological assessments, functional and psychological tests before (T0) and at the end of the intervention (T1). Data will be collected anonymously by assigning each participant a random ID number.

Measurements:

Anthropometric parameters:

- Height
- Weight
- BMI
- BIA

Physical parameters:

- Timed Up and GO (TUG);
- 30 Seconds Chair Stand Test (30" CST);
- 2 Minutes Step Test (TMST);
- Back Stretch Test;
- Chair Sit and Reach Test;
- Handgrip Strength Test (HGS).

Psychological Parameters:

- The State-Trait Anxiety Inventory (STAI-Y);
- Beck Depression Inventory (BDI);
- Fatigue Severity Scale (FSS);
- The EORTC Core Quality of Life questionnaire (EORTC QLQ-C30);
- Brief COPE.

Experimental Design

After initial evaluations, subjects will be randomly assigned to one of two groups. All protocols will last 24 weeks and will be conducted at the Angiulli Artistic Gymnastics Society (Bari).

Sessions will be conducted in small groups. These groups will be closely supervised by exercise professionals, adapted physical activity (AFA) specialists to ensure the safety of the participants, maintain the right level of intensity, and correct execution technique. To monitor and adjust the training intensity (internal load) during the ongoing sessions, Borg's Fatigue Perception Scale (RPE) (6-20) (Borg, 1982) will be used at the end of each exercise set to adjust the load in Borg = 10-15 points (Gary Liguori & American College of Sports Medicine (ACSM), 2021). Participants will be previously familiarized with the scale.

Participants in the WLCG will not perform any structured physical activity during the entire intervention period, maintaining their usual lifestyle and placed on a waiting list to receive adapted physical activity after the 24-week intervention period.

Multi-component Training:

Each training session will include an initial 10-minute muscle activation phase (low-intensity walking, Borg = 10-11) to increase heart rate, improve muscle blood flow, and prepare the major joints for the next phase of work, a 40-minute main period of exercise (aerobic exercise, mobility exercises, and resistance training), and a 10-minute defatigue period (breathing and stretching exercises). Cardiorespiratory training will consist of progressive aerobic exercises: controlled and rhythmic jumping jacks, step-ups on a stable platform (such as a low step or stable surface), alternating knee lifts, quick side steps or lateral leg lifts. Finally, 3 minutes of low-intensity walking to facilitate recovery for the next phase of training.

Mobility training will consist of specific exercises (chest extensions, cat to cows, overhead stretching with stick, and active internal rotation of the hips) targeting the major joints, performed at maximum (1 to 3 sets) but avoiding pain. Duration will gradually increase from 30 to 60 seconds per repetition, repeating one to three times. Providing recovery intervals of 30 to 60 seconds between sets and exercises.

The counter-resistance training will consist of exercises targeting the different muscle groups (8 exercises): quadriceps (leg extensions with ankle bar/half squat with chair), biceps brachii (unilateral curl with dumbbell), shoulders (shoulder press with dumbbell), triceps brachii (french press with dumbbell), pectorals (dumbbell chest press/dumbbell flies), and back (dumbbell paddles). The counter-resistance training program will follow the principle of gradual progressive loading. Initially, participants will perform one set of 10-15 repetitions, which will increase to three sets of 10-15 repetitions, over the course of the intervention. Load adjustments will be made to ensure that the perception of effort (RPE) remains between 13 and 15 points on the Borg Scale (6-20). During the protocol, participants will be provided recovery intervals of 60 to 120 seconds between sets and

exercises. To prevent premature muscle fatigue, exercises were performed using an alternating training method based on the division of muscle groups (upper muscle exercises will be performed in the first session and lower muscle exercises in the second).

The cool-down period will consist of breathing and stretching exercises. Stretching will be performed seeking maximum stretch on all major muscle groups (1 to 3 sets per muscle group) while avoiding joint pain. The duration will gradually increase from 10 to 30 seconds per stretch, repeating one to three times for a total of 60 seconds per exercise.

Aerobic training:

Each training session, again, will include an initial 10-minute muscle activation phase (low-intensity walking, Borg = 10-11) to increase heart rate, improve muscle blood flow, and prepare major joints for the next work phase, a 40-minute main exercise period. During the main exercise period, aerobic training will consist of 25 minutes of progressive aerobic exercises: controlled and rhythmic jumping jacks, step-ups on a sturdy platform (such as a low step or stable surface), standing knee raises (alternating legs), fast side steps or side leg raises. This will be followed by 15 minutes of walking. Exercises will be performed at an intensity to ensure that perceived exertion (RPE) will remain between 13 and 15 points on the Borg Scale (6-20). Progression over the weeks will be by maintaining the intensity in this range. The main goal of this phase will be to maintain a constant duration of exercise, increasing the intensity gradually.

The cool-down period will consist of breathing and stretching exercises on all major muscle groups (1-3 sets per muscle group) while avoiding joint pain. The duration will be gradual, 10 to 30 seconds per stretch, repeated one to three times for a total of 60 seconds per stretch.

EXPECTED RESULTS AND RELEVANCE

Although the positive effect of physical activity in cancer survivors currently in physiological or chronic-stabilized condition has already been demonstrated, the impact of integrating multiple exercise modalities into an MCT or TA, remains poorly explored. It is still not entirely clear what may be the most efficient protocol for improving physiological and psychological parameters in cancer survivors. At the end of this exercise program, we expect to find an overall improvement in physiological, motor and psychological parameters, with a greater increase in the MCT group. Furthermore, we believe that this new research modality may provide a new approach to propose

physical activity that is particularly engaging, motivating, and designed to improve quality of life (physiologically and psychologically). To date, exercise remains an essential factor in promoting psychological and biological improvements with profound implications for public health. Indeed, physical activity promises to be an important tool to be used alone or in combination with traditional therapies (such as drugs or medicines) to increase the effectiveness of strategies for prevention and treatment of various chronic noncommunicable diseases.

Critical situations and possible adverse effects

Rare but considered major risks could include:

- Acute cardiovascular events: participants could, in rare cases, be subject to episodes of angina, arrhythmias, or increased blood pressure during exercise sessions.
- Falls or injuries: the proposed exercises, if performed incorrectly or without supervision, could present a risk of falls or musculoskeletal injuries.

Risk Management Strategies:

- Continuous monitoring during sessions: each training group will be supervised by trained professionals in adapted physical activity (AFA). Borg scale will be used to monitor perceived exertion during exercise, keeping it in a moderate range (10-15 points).
- Emergency procedures: to ensure safety, an emergency plan will be available. AFA workers are adequately trained in order to recognize any symptoms of fatigue or cardiovascular discomfort and to intervene promptly if necessary.
- Medical support: before starting, participants will provide an exercise fitness assessment signed by the relevant physician cardiologist, ensuring that they are fit to participate. In addition, the proximity (approximately 3 minutes by car, 1.4 km) to the main local medical facility (Policlinico di Bari - azienda ospedaliero universitaria consorziale policlinico, [name]) was considered to allow quick access to emergency services.

Documentation in the Research Protocol:

All preventive measures and management strategies are included in the protocol:

- Structure of training sessions, control of exercise intensity, and supervision by qualified personnel are provided in the “intervention” section.
- Cardiovascular and musculoskeletal risk management is addressed in the inclusion/exclusion criteria, which exclude participants with acute or unstable conditions to ensure the safety of the study sample.

REFERENCES

Aaronson, N. K., Ahmedzai, S., Bergman, B., Bullinger, M., Cull, A., Duez, N. J., ... & Takeda, F. (1993). The European Organization for Research and Treatment of Cancer QLQ-C30: a quality-of-life instrument for use in international clinical trials in oncology. *JNCI: Journal of the National Cancer Institute*, 85(5), 365-376.

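### The inclusion list asks for remission and for current treatment without saying whether these are alternatives, which conflicts with the target population; treatment status is then neither recorded nor used

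*Combined protocol and SAP*

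**What the plan says.** Under PARTICIPANTS, Inclusion criteria, two separate bullets of one list read "Subjects in remission for at least 3 months" and "Currently in treatment, as long as not hospitalized, in stabilized chronic condition". No connector or heading marks them as alternatives. The protocol does not define remission, treatment or a stabilized chronic condition.

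The population is described in three other places:

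- PARTICIPANTS, opening sentence: "The study aims to recruit at least 60 cancer survivors currently in physiological or chronic-stabilized condition between 18-80 years of age".
- EXPECTED RESULTS AND RELEVANCE repeats the 'or' when it says that the benefit of physical activity in "cancer survivors currently in physiological or chronic-stabilized condition has already been demonstrated".
- The purpose statement refers only to stability: "in cancer survivors currently in a stabilized condition, compared to an aerobic training protocol (AT) and a waiting control group (WLCG").

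On allocation, PROCEDURES states "Then participants will be randomly assigned to one of three groups", while Experimental Design states "After initial evaluations, subjects will be randomly assigned to one of two groups". Neither names a stratification or balancing factor. The measurements listed for T0 and T1 are anthropometric, physical and psychological; treatment status is not among them. SAMPLE NUMEROSITY does not mention it, and the document describes no covariate or subgroup analysis by it.

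**The concern.** Inclusion items are cumulative by convention, and others in this list (performance status, consent, sedentary lifestyle) plainly are. A screener who applies the two bullets in the same way enrols only people who are both in remission and on treatment. A screener guided by the population sentence enrols people who are either. Two screeners could therefore admit different people from the same list, and a reader of the results could not tell to whom they apply.

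The either/or reading raises a second question. The protocol's introduction attributes fatigue, depression, loss of aerobic capacity, strength and flexibility, and poorer quality of life to cancer treatment. It puts fatigue at up to 70% of patients during chemotherapy and radiation therapy. The trial measures these same domains with the FSS, BDI, QLQ-C30, step test, handgrip and flexibility tests. By the protocol's own account, then, being on treatment is likely to be prognostic. As written, though, the trial would have no planned record of it, so an imbalance between arms could be neither seen nor adjusted for.

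**Working it through.** **Step 1: the two readings against the stated population.**

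| Person | Both bullets required | Either bullet sufficient | Consistent with the 'or' in the population sentence |
|---|---|---|---|
| In remission at least 3 months, treatment finished | excluded | eligible | should be eligible |
| On treatment, stable, not in remission | excluded | eligible | should be eligible |
| In remission and on some ongoing therapy | eligible | eligible | eligible |

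The last column takes the physiological condition to mean the remission group and the chronic-stabilized condition to mean the on-treatment group. That is the natural mapping, since the treatment bullet uses the stabilized-chronic wording, but the protocol does not state it. The joint reading disagrees with the population sentence in the first two rows. The alternative reading agrees in all three.

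**Step 2: does any later text handle a mixed population?** The inputs to the sample-size calculation are an effect size ("assuming a mean effect (with a value of 0.25 for effect size f"), significance level 0.05, power 0.85, two groups, two times, correlation 0.5 and a nonsphericity correction of 1. None concerns treatment status. The allocation text, the measurement list and the rest of the document contain nothing on it either.

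**Step 3: how often would arms differ by chance?** The plan gives no figure on this point, so there is none to reproduce. Inputs:

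- n = 20 per arm, from the minimum of 60 divided by 3 groups. Equal allocation is assumed; the protocol states no ratio.
- p = share of participants on treatment. The protocol does not give it; 20%, 30% and 50% are assumed, with 10% as a low case.
- A notable imbalance is a difference of 4 or more patients between two arms, that is 4/20 = 20 percentage points.

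Let X and Y be independent Binomial(20, p) counts for two arms, with simple unstratified allocation. Then P(|X − Y| ≥ 4) is the sum of P(X = i)·P(Y = j) over all i, j from 0 to 20 with |i − j| ≥ 4.

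| Assumed share p | P(two given arms differ by 4 or more) |
|---|---|
| 10% | 6.3% |
| 20% | 16.4% |
| 30% | 22.6% |
| 50% | 26.8% |

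**Step 4: how much would such an imbalance matter?** The frequency in step 3 is not a measure of harm. Suppose treatment status shifts the T0–T1 change by 0.3 to 0.5 SD of change (assumed; not in the protocol). A 20-point imbalance then moves the contrast between two arms by 0.20 × 0.3 = 0.06 SD to 0.20 × 0.5 = 0.10 SD. The standard error of that contrast with 20 per arm is √(1/20 + 1/20) = 0.316 SD. The shift is therefore 0.06/0.316 = 0.19 to 0.10/0.316 = 0.32 of one standard error.

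**The case against.** The strongest reply is that the intended meaning can be recovered. The treatment bullet carries a proviso about hospitalization and reads like a permission. The bullet admitting women and men is also a statement of scope, so not every item in the list narrows it. The 'or' appears twice, and the introduction says exercise helps during as well as after treatment, so mixed enrolment looks deliberate. A broad population is a legitimate choice, and the performance-status limit, the exclusion of metastasis and the specialist clearance narrow it. This makes the either/or reading the more likely one. It does not remove the conflict: an eligibility list has to be applicable as written, and this one is not.

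A reader might infer that the list admits almost nobody. The documents do not support that. Neither term is defined, the bullets are not mutually exclusive, a person in remission on ongoing therapy meets both, and no count of such people is given. For the same reason one cannot say that the list defines the wrong population, only that it is inconsistent with the one stated.

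A reader might also infer that unstratified mixing biases the comparisons. It does not. Under randomization, chance imbalance is random error that the standard error already reflects. An analysis of change would also remove stable differences in baseline level, leaving only an effect of status on change. The step 3 calculation would apply to any unstratified baseline factor, and the missing covariate is one instance of a wider gap, since the document contains no analysis-model section. These points stand. They make stratification optional, but they do not argue against recording the status and adjusting for it.

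**Conclusion.** The concern holds as a conflict between a stated rule and a stated population. Read cumulatively, the two bullets exclude two groups that the population wording appears to include. Read as alternatives, they admit people on and off treatment, while the plan neither records the difference nor uses it, although its introduction links treatment to the domains it measures.

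The first part rests on the text alone. The size of the second depends on assumptions: equal allocation of 60, and an unknown on-treatment share. Over assumed shares of 20% to 50%, two arms would differ by 20 percentage points or more in about 16% to 27% of trials. On the illustrative effects in step 4, the resulting shift is a fifth to a third of one standard error: a loss of precision worth a cheap remedy, not a threat to the validity of the randomized comparison. The point should be corrected, chiefly because eligibility decides whom the results describe.

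**What to change.** 1. Reconcile the two bullets with the population sentence. State whether they are alternatives or joint requirements; if only one group is meant, delete the other bullet. Define remission and treatment. Which group or groups to enrol is for the sponsor to decide. Bring the purpose statement, the population sentence and the expected-results section into line with the decision.
2. If the bullets are alternatives, add treatment status (on or off) to the items recorded at T0 and prespecify it as a covariate in the outcome models.
3. Optionally, stratify allocation by the same two-level factor. This first requires the number of groups to be settled, because the protocol gives both two and three.

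The cost is one amended criterion, one recorded baseline item and one model degree of freedom. Stratification, if chosen, adds one two-level stratum to the allocation. No extra participants or visits are needed.

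### Dropout is foreseen, but the plan has no as-randomised rule and no rule for a missing T1, and the only analysis it implies by default keeps only participants with both T0 and T1

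*Combined protocol and SAP*

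**What the plan says.** Under Purpose and Hypothesis, the secondary outcome is "To assess adherence to protocols through analysis of dropout rates and number of sessions completed". The plan therefore foresees that some participants will leave, although it predicts no rate.

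Under Procedures, participants are randomised to MCT, AT or WLCG. The Data collection paragraph sets two assessments: "All subjects will participate in physiological assessments, functional and psychological tests before (T0) and at the end of the intervention (T1"). Experimental Design puts 24 weeks between them. There is no interim visit.

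The document has no statistical analysis section. The nearest thing is Sample Numerosity, where "two groups (multicomponent training and aerobic training) and two measurement times (before and after the intervention) were considered". That section also gives an effect size f of 0.25 and these inputs: "A significance level of 0.05 was set", "a statistical power of 85% (0.85) was adopted", "An average correlation (0.5) was estimated between the repeated measurements on participants" and "setting a correction for nonsphericity equal to 1". It concludes that 32-40 participants are needed, 16-20 per group. Recruitment is set at no fewer than 60.

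The document does not define an analysis set, state how a missing T1 is handled, say whether people who stop training are still called to T1, or allow for dropout in the sample size.

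**The concern.** People who leave a 24-week supervised exercise programme are unlikely to be a random subset. WLCG members have no programme to leave, so loss of T1 can plausibly differ by arm. An analysis restricted to participants with both measurements then compares groups that randomisation no longer protects. It could create or hide a benefit of training.

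The gap also leaves the choice of analysis set and missing-data method open until the data are seen. A person who drops out would count as non-adherent in the secondary outcome and could disappear from the primary comparisons.

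**Working it through.** **1. Which analysis do the inputs imply?** Inputs from Sample Numerosity: f = 0.25, alpha = 0.05, power 0.85, k = 2 groups, m = 2 times, rho = 0.5, nonsphericity correction 1. For the group-by-time interaction, G*Power uses

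lambda = f² × N × m / (1 − rho) = 0.0625 × N × 2 / 0.5 = 0.25 N, with df 1 and N − 2.

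The smallest N with 85% power is 38 (85.1%), inside the stated 32-40. The between-groups variant needs 110 and does not fit. (The within-factor variant also gives 38.) The implied analysis is therefore a 2 × 2 repeated-measures ANOVA. With two times, its interaction test is a two-group comparison of T1 − T0, and in standard form it needs both values.

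For scale, a comparison of mean change with N/2 per arm has lambda = N × d² / 4. Setting this equal to 0.25 N gives d = 1, so the planned MCT-AT difference is one SD of change.

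**2. Bias from outcome-related loss.** The documents give no dropout rate, so every rate here is an assumption. Suppose there is no true effect, and the fraction p of an arm lost is the lowest part of a latent tendency to stay that correlates r with change. Those remaining have mean change

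shift = r × phi(z_p) / (1 − p),

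where z_p is the p-quantile of the standard normal distribution and phi its density. The multiplier phi/(1 − p) is 0.195, 0.350 and 0.497 at p = 10%, 20% and 30%.

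| Loss in trained arm (none in WLCG) | Shift, r = 0.5 | Shift, r = 0.7 |
|---|---|---|
| 10% | 0.10 SD | 0.14 SD |
| 20% | 0.18 SD | 0.25 SD |
| 30% | 0.25 SD | 0.35 SD |

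In simulation with 20 per arm, the nominal 5% test then rejects about 6%, 8% and 11% of the time at r = 0.5, and about 7%, 11% and 17% at r = 0.7.

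Milder contrasts use the difference of two shifts, here with r from 0.3 to 0.5:
- 20% against 5% loss: 0.07-0.12 SD.
- 30% against 10% loss: 0.09-0.15 SD.
- Equal loss by the same mechanism: 0.

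**3. Bias from T0-related loss.** Let leaving depend on a low T0 instead (r = 0.7, 20% loss). The remaining T0 mean rises by 0.7 × 0.350 = 0.245 SD. The slope of change on T0 is rho − 1 = −0.5, so the change contrast moves by −0.12 SD. Adjusting T1 for T0 brings this to about 0.

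**4. What T0 adjustment does not do.** Under the mechanism of step 2, simulation with 20 per arm shows the shift falling only from about 0.16 to 0.12 SD (r = 0.5, 20% loss) and from about 0.33 to 0.25 SD (r = 0.7, 30% loss). About three quarters of the bias remains.

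A mixed model with a common T0 mean does no better. With only two times, T0-only participants inform the shared T0 mean, which cancels from the arm contrast. Fits of both models to simulated data with missing T1 agreed to six decimals.

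**5. Power for MCT against AT, from 20 per arm.** Equal allocation is assumed; the documents give no ratio. The variance of change is 2(1 − rho) = 1. The variance of T1 given T0 is 1 − rho² = 0.75. The adjusted analysis therefore has lambda = 0.25 N / 0.75, with df 1 and N − 3.

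| Loss | N with T1 | lambda, unadjusted | Power | lambda, T0-adjusted | Power |
|---|---|---|---|---|---|
| 0% | 40 | 10.0 | 86.9% | – | – |
| 10% | 36 | 9.0 | 83.0% | 12.0 | about 92% |
| 20% | 32 | 8.0 | 78.1% | 10.7 | about 88% |

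**The case against.** **The plan names no analysis model.** A reader might infer that it commits to a completers-only comparison of all three arms. It does not. Completers-only is the default of a method inferred from sample-size inputs, and those inputs cover MCT and AT only. Extending the point to WLCG rests on the three-arm design and the common T0/T1 schedule. This objection stands, and it limits the point to a default that nothing in the plan overrides.

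**T1 is intended for everyone.** The Data collection paragraph schedules T1 for all subjects, and the exclusion criteria remove people who expect to be away for more than two weeks. Stopping training is not the same as missing T1, and actual loss may be small. That is fair, and the 10-30% range has no support in the documents. But the plan does not say that T1 is sought from those who stop, nor what is done if it is not obtained.

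**The bias figures are an extreme case.** They assume no loss in WLCG. A reader might also infer a spurious MCT-AT difference of similar size. The documents give no reason to expect different loss in the two trained arms, and equal loss by the same mechanism gives none.

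**Dropout does not by itself make the trial underpowered.** The fall to 78.1% belongs to the unadjusted analysis. With T0 adjustment, power stays above the planned 85% even at 20% loss.

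**Conclusion.** The omission is real: dropout is an outcome, yet the plan has neither an as-randomised statement nor a rule for a missing T1. The analysis it implies would by default drop participants without T1 and ignore T0.

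The possible bias is about 0.1 to 0.35 SD of change, against a planned MCT-AT difference of 1 SD. That range rests on assumed loss of 10-30% in a trained arm, none in WLCG, and a correlation of 0.5-0.7 between staying and change. It shrinks as loss becomes similar across arms and vanishes when loss and mechanism are equal.

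The documents do not show that such bias will occur. A reader might also infer that a mixed model would bring dropouts back into the comparison. With only T0 and T1 it cannot: it removes bias from T0-related loss, but most of the bias from outcome-related loss remains. Obtaining T1 from people who stop is the main protection. The plan should be changed before analysis.

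**What to change.** 1. State that every participant is analysed in the arm assigned, regardless of attendance. Make explicit that the T1 tests already intended for everyone are also sought at week 24 from those who stopped training.
2. Compare arms at T1 with adjustment for T0, or with the equivalent common-baseline mixed model, in place of the unadjusted repeated-measures contrast. This deals with T0-related loss and, at the plan's own correlation of 0.5, cuts residual variance from 1 to 0.75. Do not describe it as recovering the T1 information of dropouts.
3. Add a sensitivity analysis that shifts missing T1 values in the trained arms over a stated range, with a reason given for the range.
4. State power for the number expected to have T1 under the analysis actually chosen, with dropout labelled as an assumption. The table in the working gives figures for 10% and 20% loss.

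**Cost:** a few sentences in the plan and a little more analysis per measure. No visit is added beyond the T1 already intended, though some effort is needed to bring back people who stopped. The as-randomised estimate includes non-attenders and will usually be smaller than a completers estimate.
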